### 7.10 Withdrawal of trial treatment

Patients showing an unacceptable degree of disease activity (not achieving a PsARC response) beyond week 12 and before the week 24 assessment may be withdrawn from study medication (i.e.: trial intervention) at the discretion of the chief investigator (or medically-qualified delegate) and treated as clinically indicated. At week 24 patients with MDA will continue with their allocated treatment and undergo further assessments as per protocol (see [section 5.1](#)).

Patients **MUST** be withdrawn from the study treatment if any of the following occur:

- Pregnancy
- Grade 4 or 5 systemic toxicity (see [appendix 2](#)) or a serious adverse event (SAE) thought to be related to study treatment and not alleviated by symptomatic treatment after cessation of the IMP for up to 2 weeks.
- Recurrent serious infection requiring parenteral (intravenous or intramuscular) antimicrobial agents or hypotension suggestive of impending sepsis syndrome.
- Confirmed blood dyscrasia or a demyelinating disorder (such as multiple sclerosis or optic neuritis)
- Lack of patient compliance with the trial intervention ([section 7.3](#))
- If missing 2 or more consecutive IMP doses.
- When visit attendance during period 1 of the trial (between week 0 and week 24) is delayed by more than 10 days of the mandated window visit date (see also timeline reference in the summary schedule of study assessments, [section 8.6](#))

REC: 14/EM/0124

- Withdrawal of consent (during either interventional period or observational period, see [section 8.6](#))
- Chief Investigator decision

All patients recruited to this study, irrespective of therapy change (as outlined above) will continue to be followed up for the 52 week study duration with imaging and immunological studies as per protocol, with the exception of those who withdraw consent to continue with study assessments.

As far as possible, all examinations scheduled for the final study day must be performed on all subjects who receive the investigational product but do not complete the study according to protocol.

The investigator must make every effort to contact subjects lost to follow-up. Attempts to contact such subjects must be documented in the subject's records (e.g., times and dates of attempted telephone contact, receipt for sending a registered letter).

#### 7.10.1. General/study-related withdrawal criteria

- When personal circumstances mean that the regular visits required by the protocol can no longer be guaranteed
- Inability of the subject to comply with study requirements
- If intercurrent disorders develop which rule out continuation of study medication i.e. determination by the investigator that it is no longer safe for the subject to continue therapy
- If disallowed drugs are administered (see [section 7.6.3](#)).
- If a SAE occurs, the patient could be withdrawn at the discretion of the investigator.

## METHODS OF ASSESSMENT

### 8.1 Assessment of primary efficacy variable

PASDAS is a recently developed composite measure of disease activity in Psoriatic arthritis that is represented by a single score and which provides quantitative measures of improvement based on baseline scores and changes from baseline. The PASDAS has been shown to perform well not only in polyarticular but also oligoarticular PsA (34).

The PASDAS will not be performed at the bedside when assessing participants as it is a composite measure. Individual components will be assessed to allow calculation of the PASDAS at the time of data analysis as only an outcome measure. Its formula is calculated as follows:

PASDAS= (((0.18 x  $\sqrt{\text{Physician global VAS}}$ ) + (0.159 x  $\sqrt{\text{Patient global VAS}}$ ) - (0.253 x  $\sqrt{\text{SF36 - PCS}}$ ) + (0.101 x LN (Swollen joint count + 1)) + (0.048 x LN (Tender joint count + 1)) + (0.23 x LN (Leeds Enthesitis Count + 1)) + (0.377 LN (Tender dactylitis count + 1)) + (0.102 x LN (CRP + 1)) + 2) \* 1.5.

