## **11.9 Determination of sample size and randomization method**

Using in-house unpublished data we estimated the minimum clinically important difference to be 0.7 units on the PASDAS; this is similar to a published value for smallest detectable difference of 0.8 units (11). We will aim to detect a difference of at least 1 unit between the treatment arms in this study. The standard deviation of PASDAS in the TICOPA MTX rapid escalation arm (56, 57) at 24 weeks (restricted to patients who remained on methotrexate throughout) was 1.57. Assuming  $\delta=1$ ,  $\sigma=1.57$ , at alpha=0.05 and 1-Beta=0.8 this would require 78 patients. Originally the sample size for the trial was adjusted to account for 10% drop-out, requiring a total of 88 (44 per group). However, because recruitment had been slower than anticipated, in part due to the SARS-CoV-2 pandemic, drop-out was reassessed once 76 participants had the opportunity to reach the primary endpoint. Only 4 (5%) had withdrawn from follow-up prior to that point. Therefore, the total required sample size was revised down to 84 (42 per group) i.e. allowing for 5% drop-out.

For the whole-body MRI subset, published rules of thumb for pilot studies indicate that between 12 and 30 patients per group should be included. We will aim to continue recruiting patients into the WB-MRI subset until there are at least 30 patients (15 per group) with scans available at both baseline and week 24, at which point WB-MRI will cease to be performed in the remaining patients.

To estimate the ICC between two repeated readings of the PASDAS composite index with a confidence interval of width 0.2, we would need 31 patients assuming the ICC is 0.85. For the patient's global assessment of disease activity VAS, which provides the greatest loading on the PASDAS score, ICC = 0.87(35). We will aim to obtain data from at least 31 patients.

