GOLMePsA

STATISTICAL ANALYSIS PLAN

Protocol Title:	An investigator-initiated double-blind, parallel-group randomised controlled trial of GOLimumab and Methotrexate versus Methotrexate in very early PsA using clinical and whole body MRI outcomes: the GOLMePsA study
Protocol Number:	RR13/10782
Protocol Version:	8.0
Protocol Date:	09/03/2022
SAP Author:	[name]
SAP Version:	4.0
SAP Date:	15/11/2023

CONFIDENTIAL

SAP REVISION HISTORY

Protocol version	Updated SAP n°	Section changed	Description of and reason for change	Date changed
6.0	1.0	N/A	Original SAP dated 23/07/2018	N/A
7.0	1.1	N/A	Amended SAP not finalised as some of the changes to protocol needed to be reversed in a further amendment	16/09/2019
8.0	2.0	Approvals	Statistician signature added to approvals page	08/02/2022
		Abbreviations	List of abbreviations updated	10/03/2022
		3.1	Secondary objectives updated and exploratory objectives added, to match amended protocol	03/02/2022
		3.2	Secondary endpoints updated and exploratory endpoints added, to match amended protocol	03/02/2022
		3.3.2	Efficacy variables updated, to match amended protocol	03/02/2022
		3.3.3	Safety variable wording amended, to match amended protocol	03/02/2022
		4.2	Key exclusion criteria amended, to match amended protocol	03/02/2022
		5.2	Timing of analyses section updated to state that analyses involving only screening and/or baseline data will be performed as soon as all relevant data has been collected, cleaned and locked	03/02/2022
	6		Sample size amended to allow for 5% drop-out instead of 10%; details of sample size required for WB-MRI added now that this is deemed an exploratory endpoint, only available for a subset of patients	03/02/2022
	8.2		Visit window details added; clarification that MI only to be used to primary and secondary outcomes; detail regarding imputation for count data added; detail regarding MI with respect to interactions added; reference to mixed modelling added to match protocol	10/02/2022
	8.7		Derivations of US and MRI variables updated to match protocol	10/02/2022
	10.3.1		Reference to summaries of continuous variables removed as all planned variables are categorical	10/02/2022
	10.3.3		Patient global VAS added to list of PsA specific baseline variables to match protocol	10/02/2022

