	8.6		Added clarification that the assessment of predictors/modifiers of treatment response will be made for response at 24 weeks	27/06/2023
	8.7		Typo in derivation of PASDAS corrected Typo in range of LDI corrected; description of calculation expanded to match development paper MDA criterion corrected to include BSA, to match development paper Joint and enthesal remission criteria corrected to match protocol Definitions of CPDAI 'not involved' category added; typos in criteria for scores of 2 & 3 corrected	20/06/2023 20/06/2023 20/06/2023 20/06/2023 20/06/2023
	9.2		Key exclusion criteria for derivation of per protocol population amended to include receipt of systemic steroids within 4 weeks prior to screening	20/06/2023
	11.3		References to exploratory subset analyses using 76/78 joints for the secondary outcomes MDA and ACR response removed, as the intention is to focus solely on PsARC response. Correction to planned correlation between joint counts and total US GLOESS, which will be assessed using screening values rather than baseline values, as US was performed at screening rather than baseline	27/06/2023
	12.4		Initial inspection of ALT results indicates skewed distributions, therefore the planned summaries have been amended accordingly, and details given as to the time-points at which the values will be summarised. References to changes from baseline have been removed in favour of summaries at each time-point.	
8.0	4.0	3.2.4	Unplanned endpoints i.e. PASDAS status and response variables, published since the inception of the trial, added in a separate section: 
• Very low disease activity (PASDAS<1.9)• PASDAS moderate or good response• PASDAS meaningful change value achieved (improvement >1.29)	09/11/2023 (post-unblinding)
	8.7		Unplanned PASDAS status and response variables, and sensitivity definitions of US remission, defined in the derived variable section	09/11/2023 (post-unblinding)

Protocol version	Updated SAP n ^o	Section changed	Description of and reason for change	Date changed
	11.4		New 'Additional unplanned analysis' section added to give details of analysis methods for unplanned endpoints and unplanned descriptive summaries	09/11/2023 (post-unblinding)

APPROVALS

Approved By:

Role: Chief Investigator

Name: [name]

Date: 17/11/2023

Signature: _____

Role: Sub-Investigator

Name: [name] [name]

Date: 17 – November - 2023

Signature: _____

Role: Trial statistician; SAP author

Name: [name]

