3.2 Study Endpoints

3.2.1 Primary Endpoint

The primary endpoint is clinical disease activity (PASDAS) at 24 weeks.

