8.7 Derived and Computed Variables

The following derived and computed variables have been initially identified. It is expected that additional variables will be required. The SAP will not be amended for additional variables that are not related to the primary target or key secondary target variables. Any additional derived or computed variables will be identified and documented in the Stata programs that create analysis files.

Table 1: Derived and computed variables

Variable Name	Description	Valid Values (Ranges)	Computation Methods, Notes or Equations
AGE at baseline	Subject age in years	18-100	=Truncate[number of days between DateOfBirth and DateOfBaseline/365.25] (0 d.p.)
BMI	Body Mass Index	10 to 60	=[Weight (Kg)/Height (m ²)]
PASDAS	Primary endpoint: Psoriatic arthritis disease activity score	0 to 10	((0.18 x vPhysician global VAS) + (0.159 x vPatient global VAS) – (0.253 x vSF36-PCS) + (0.101 x LN (66 swollen joint count + 1)) + (0.048 x LN (68 tender joint count + 1)) + (0.23 x LN (Leeds Enthesitis Count + 1)) + (0.37 x LN (Tender dactylitis count + 1)) + (0.102 x LN (CRP + 1)) + 2)*1.5 See section 15 for details of SF36 PCS calculation
BASDAI	Bath Ankylosing Spondylitis Disease Activity Index	0 to 10	BASDAI=((sum Q1:Q4)+((Q5+Q6)/2))/5
Enthesitis score	Leeds Enthesitis Index	0 to 6	Each of six sites scored (0=absent, 1=present) for enthesitis: medial femoral condyle (2), Achilles tendon (2), plantar fascia insertion (2)
Dactylitis score	Leeds Dactylitis Index	0 to approx. 400	Once the presence of dactylitis is established in each digit, the ratio of the circumference of the affected digit to the circumference of the digit on the opposite hand or foot is measured. If the contralateral digit is also affected then the sex-specific standard reference value corresponding to the digit is used instead. The digit result is then obtained by subtracting 1 from the ratio, multiplying by 100, then multiplying the result by the tenderness score for that digit. The results of each digit are then added to produce a total score

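### The PASDAS formula gives the tender-dactylitis weight as 0.377 in the protocol and 0.37 in the SAP: a minor inconsistency in the primary endpoint's definition, to be reconciled and reported

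*Protocol*

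**What the plan says.** SAP 3.2.1 states: "The primary endpoint is clinical disease activity (PASDAS) at 24 weeks". Protocol 8.1 explains that PASDAS is not scored at the bedside. Its components are recorded and the score is computed at analysis, so the written formula is the specification for the code.

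The two formulas differ in one weight:

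- Protocol 8.1: "0.377 LN (Tender dactylitis count + 1"
- SAP 8.7, Table 1: "0.37 x LN (Tender dactylitis count + 1"

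The SAP's front page gives "Protocol Version: 8.0" as the protocol it was written against, so this is not a comparison with a superseded protocol. The SAP revision history, under SAP version 3.0, records "Typo in derivation of PASDAS corrected". The entry is dated 20/06/2023, after protocol 8.0 (09/03/2022). It does not say which typo was corrected, and the current SAP table reads 0.37.

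**The concern.** The formula produces the week-24 outcome and the baseline covariate in the primary ANCOVA. It also produces the secondary PASDAS scores at 12, 36 and 52 weeks, the test-retest reliability estimate and the PASDAS state and response variables. A programmer following the protocol and one following the SAP would get different scores for every patient with at least one tender dactylitic digit.

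What is at stake is exact reproducibility. Someone who recomputes the primary score from the protocol formula may not recover the reported values and would not know why.

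**Working it through.** **1. Term-by-term comparison of the numerical weights**

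| Term | Protocol 8.1 | SAP 8.7 |
|---|---|---|
| Physician global VAS (square root) | 0.18 | 0.18 |
| Patient global VAS (square root) | 0.159 | 0.159 |
| SF-36 PCS (square root, subtracted) | 0.253 | 0.253 |
| Swollen joint count | 0.101 | 0.101 |
| Tender joint count | 0.048 | 0.048 |
| Leeds enthesitis count | 0.23 | 0.23 |
| **Tender dactylitis count** | **0.377** | **0.37** |
| CRP | 0.102 | 0.102 |
| Constant; multiplier | +2; 1.5 | +2; 1.5 |

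Only one weight differs, so the SAP is not using a different version of the index. The weight is an external constant and cannot be re-derived from the documents. Only the size of the disagreement can be calculated.

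**2. Difference per score**

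1.5 x (0.377 - 0.37) x ln(count + 1) = 0.0105 x ln(count + 1)

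The reference values are in protocol 11.9: the "minimum clinically important difference to be 0.7 units on the PASDAS" and the SD ("restricted to patients who remained on methotrexate throughout) was 1.57").

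| Tender digits | Shift (units) | % of 0.7 | % of SD 1.57 |
|---|---|---|---|
| 0 | 0 | 0 | 0 |
| 1 | 0.0073 | 1.0 | 0.5 |
| 2 | 0.0115 | 1.7 | 0.7 |
| 3 | 0.0146 | 2.1 | 0.9 |
| 5 | 0.0188 | 2.7 | 1.2 |
| 10 | 0.0252 | 3.6 | 1.6 |
| 20 (assumed maximum) | 0.0320 | 4.6 | 2.0 |

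Two complete scores show the scale. The inputs are assumed: both VAS 50, PCS 35, 5 swollen joints, 8 tender joints, enthesitis count 2, CRP 10. With one tender digit PASDAS is 5.918 (weight 0.377) or 5.911 (weight 0.37). With four it is 6.436 or 6.419.

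**3. Effect on the difference between arms**

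The unadjusted week-24 difference moves by 0.0105 times the between-arm difference in mean ln(count + 1). A movement of 0.01 units would need that difference to be 0.01 / 0.0105 = 0.95, a ratio of e^0.95 = 2.6 in the geometric mean of (count + 1). The documents give no dactylitis counts by arm, so this is a condition and not an estimate. The baseline covariate is computed with the same weight in both arms.

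**4. Effect on the sample size**

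The plan's figure reproduces. With a difference of 1, SD 1.57, two-sided alpha 0.05 and power 0.80:

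n per arm = 2 x (1.960 + 0.842)^2 x 1.57^2 / 1^2 = 38.7, rounded up to 39, total 78 (power 0.803)

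Allowing for drop-out, 39/0.90 rounds up to 44 per arm (88) and 39/0.95 to 42 per arm (84), as stated. The dactylitis weight is not an input. As an extreme bound, suppose the target difference fell by the whole 0.032, which would need 20 tender digits in every patient of one arm and none in the other. Power at 39 per arm would go from 0.803 to 0.777.

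**5. Effect on categories**

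SAP 8.7 defines PASDAS cut-offs at 1.9, 3.2 and 5.4, and improvement cut-offs at 0.8, 1.29 and 1.6. A status can change only if the score lies within about 0.03 units of a cut-off. An improvement score shifts only if the dactylitis count changed from baseline. SAP 3.2.4 and 11.4 place all these variables among the endpoints added after unblinding and treat them as exploratory.

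**The case against.** The strongest reply has three parts.

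*The operative formula is not in doubt.* The SAP is the computation specification. It is later than the protocol, its brackets balance, it names the 66/68 joint counts, and its authors revisited the PASDAS derivation in version 3.0. This stands as far as it goes: the SAP is the natural candidate for what was programmed. It does not show that 0.37 is the correct weight, because the log does not identify the typo.

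*The mismatch may be a misprint or an artefact of reading the PDF.* The protocol's dactylitis term is the only weighted term without a multiplication sign, and the extra 7 stands where the sign should be. One bracket in the protocol formula is also never closed. This is possible but unproven. It is equally possible that the SAP dropped a digit.

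*The effect is negligible.* Numerically this is right, and it sets the severity. It is no reason to leave two formulas for the primary endpoint in place.

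A reader might infer more than the documents support:

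- That the primary result is in jeopardy. Steps 3 and 4 rule out a material effect.
- That planned responder endpoints could be misclassified. The PASDAS cut-offs serve only the unplanned, exploratory endpoints.
- That the protocol value is right and the SAP's a slip, or the reverse. Neither can be shown from these documents.

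**Conclusion.** The inconsistency is real, is in the current text of both documents, and concerns the formula for the sole primary endpoint and its baseline covariate. One printed weight is wrong, provided the protocol's printed page does read 0.377. Which one is wrong cannot be settled here.

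Severity is minor. The shift is at most about 0.032 units in an individual score, under 5% of the stated minimum important difference. It moves the difference between arms by less than 0.01 units unless the arms differ by about 0.95 or more in mean ln(count + 1). The maximum of 20 tender digits is an assumption. The point concerns exact reproducibility of the primary score and does not threaten the trial's conclusion.

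**What to change.** 1. Look at the protocol's original page to exclude a misreading, then check the weight against the index's development source cited in the protocol.
2. Print one formula, with the same weight, in protocol 8.1 and SAP 8.7.
3. Confirm which weight the analysis code uses. If it is not the verified one, correct it and rerun the PASDAS derivation and every analysis that depends on it.
4. State in the report which coefficient produced the primary result. SAP 4.0 already contains changes dated after unblinding, so a short clarification in the report is the practical place.

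The cost is one figure in one document and one sentence in the report, plus a rerun only if the code carries the wrong weight. No change to the design, sample size or analysis model is needed.

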### 8.2 Assessment of secondary efficacy variable(s)

#### 8.2.1. C-Reactive Protein

Standard C-reactive protein (mg/L) will be the selected acute phase reactant.

### 8.2.2 Tender joint count

The number of tender and painful joints will be determined by examination of 78 joints (39 joints on each side of the patient's body, see [appendix 7](#)). Joints will be assessed for tenderness by pressure and joint manipulation on physical examination. The patient will be asked for pain sensations on these manipulations and watched for spontaneous pain reactions. Any positive response on pressure, movement, or both will then be translated into a single tender-versus-non tender dichotomy. The same assessor should preferably perform the TJC and SJC for a given patient particularly during the first 24 weeks of the study to minimize inter-observer variation. Missing, replaced, ankylosed, or arthrodesed joints will be identified by the investigator at the Screening Visit and will be excluded from evaluation during the trial.

### 8.2.3 Swollen joint count

The number of swollen joints will be determined by examination of 76 joints (38 joints on each side of the patient's body, hip joints not encompassed, see [appendix 7](#)). Joints will be classified as either swollen or not swollen. Swelling is defined as palpable fluctuating synovitis of the joint. Swelling secondary to osteoarthritis will be assessed as not swollen, unless there is unmistakable fluctuation. Where possible, the same assessor should preferably perform the TJC and SJC for a given patient particularly during the first 24 weeks of the study to minimize inter-observer variation. Missing, replaced, ankylosed, or arthrodesed joints will be identified by the investigator at the Screening Visit and will be excluded from evaluation during the trial.

### 8.2.4 Patient's Assessment of Pain Visual Analogue Scale

The patient will be asked to assess their current level of joint pain by marking a vertical line on a 100 mm horizontal VAS where 0 represents no joint pain ("excellent") and 100 represents worst imaginable joint pain ("poor"). The Patient's Assessment of Pain VAS should be administered prior to the TJC and SJC examinations. Results will be expressed in millimetres measured between the left end of the scale and the crossing point of the vertical line; this procedure is applicable for all VAS used in the trial (see [appendix 6](#)).

### 8.2.5 Patient's Global Assessment of Disease Activity Visual Analogue Scale

The patient's overall assessment of their PsA activity will be recorded using the 100 mm horizontal VAS where 0 or left end represents "no disease activity" or "excellent" and 100 or right end represents extremely active disease "poor". The wording proposed by Cauli et al (35) referring specifically to PsA will be used (see [appendix 6](#)).

### 8.2.6 Physician's Global Assessment of Disease Activity Visual Analogue Scale

The Investigator will be asked to give an overall assessment of the severity of the patient's current PsA activity using a 100 mm horizontal VAS, where 0 at the left end represents no disease activity ("Disease not active") and 100 on the right end represents extremely active disease ("Disease extremely active"). The investigator making the assessment must be a rheumatologist or medically qualified physician. The same assessor should preferably perform the Physician's Global Assessment of Disease Activity VAS for a given patient particularly during the first 24 weeks of the study to minimize inter-observer variation.

